6.2.1.3. Incidence of Delayed Return to Usual Health

The incidence of participants experiencing ongoing symptomatic COVID-19 and post-COVID-19 syndrome will be compared between both arms.

6.2.1.4. Rate of Hospitalizations

The incidence of ER visits, acute care admissions, and ICU admissions over the 12-week study period will be compared between arms. Length of hospitalization (i.e., length of stay) will also be compared between arms; hospitalization will be defined as the time of change to inpatient status until the time of discharge (i.e., time spent in emergency will not be included in the length of stay analysis).

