2.1.2. Secondary Objectives

Secondary objectives include:

1. Effect of COVID-19 on the health status of participants
2. Symptom severity of COVID-19 symptoms, including: fever, cough, shortness of breath, fatigue, headache, myalgia/arthralgia (body aches), nausea, vomiting, diarrhea, shakes/chills, congestion, and loss of taste and smell
3. Total symptom duration
4. Incidence of delayed return to usual health
5. Frequency of hospitalizations, including: ER visits, acute care admissions, and ICU admissions
6. Hospital length of stay
7. All-cause mortality

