3.3. Inclusion/Exclusion Criteria

3.3.1. *Inclusion criteria:*

1. Adults (≥ 18) who test positive for SARS-CoV-2 by reverse transcriptase polymerase chain reaction (RT-PCR) in an outpatient setting
2. Access to internet

3.3.2. *Exclusion criteria*

1. Symptom onset greater than 7 days prior to enrolment
2. Supplementing regularly with >500 mg vitamin C, >1000 units vitamin D, >120 mcg vitamin K (any form), or >15 mg zinc taken daily within the past month
3. Currently taking warfarin or an equivalent vitamin K antagonist anticoagulant
4. End stage chronic kidney disease
5. History of calcium oxalate kidney stones
6. Active granulomatosis (sarcoidosis, tuberculosis, lymphoma)
7. Known hypercalcemia or hypervitaminosis D

8. Currently taking either of the following antibiotics: cephalexin, tetracyclines
9. Known allergy to any investigational product, silicon dioxide, cellulose, or medium chain triglyceride oil
10. Participating in an investigational study or participation in an investigational study within the past 30 days
11. Any reason which, under the discretion of the qualified investigator or delegate, would preclude the patient from participating.

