6.2.2. Statistical Methods

All analyses will follow an intention to treat approach. Continuous and quasi-continuous variables (participant-reported health & health status, primary & secondary severity analyses, and length of stay) will be compared between arms using unadjusted t-tests. Dichotomous outcomes (incidence of severe symptoms, delayed return to usual health, hospitalizations and deaths) will be compared between arms using Chi-square tests or Fisher's exact tests where appropriate. Time to symptom resolution will be displayed graphically with Kaplan-Meier curves and differences between arms will be compared with a log-rank test.

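### Length of stay is defined only for admitted participants and tested between arms, with no value for the never-admitted and no rule for death before discharge, so the comparison can point the wrong way.

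*Combined protocol and SAP*

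**What the plan says.** Section 2.1.2 lists "Hospital length of stay" as the sixth of seven secondary objectives. Section 6.2.1.4 says "Length of hospitalization (i.e., length of stay) will also be compared between arms" and gives the definition: "hospitalization will be defined as the time of change to inpatient status until the time of discharge". It adds that "time spent in emergency will not be included in the length of stay analysis", so a visit to the emergency department alone produces no stay. Section 6.2.2 names the test: "length of stay) will be compared between arms using unadjusted t-tests". The same section opens with "All analyses will follow an intention to treat approach".

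No section gives a value to a participant who is never admitted, names the analysis set for this outcome, or says how a stay that ends in death is counted. Participants are people who test positive "in an outpatient setting" (section 3.3.1), so most can be expected never to be admitted. The incidence of emergency visits, acute care admissions and ICU admissions is compared separately (sections 6.2.1.4 and 6.2.2), and so are deaths (sections 6.2.1.5 and 6.2.2).

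**The concern.** As defined, a stay exists only after an admission. An admission happens after randomisation, and the closing paragraph of the introduction hopes that treatment will make admissions rarer. If it does, the admitted participants in the two arms are different kinds of people, and randomisation no longer protects the comparison of their stays.

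If treatment prevents mainly short admissions, those left in the active arm are the longer ones. Mean stay on active then rises even though fewer days are spent in hospital. A reader of the results could take this as a sign of harm from a product that helped.

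The test would also rest on a handful of skewed values. And because the analysis set is not written down, it could be chosen after the data are seen.

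**Working it through.** **Plan's own figure.** There is none to reproduce. The documents give no expected admission rate, no expected stay and no power for this outcome. The sample size in section 5 concerns the primary outcome only. It is used here solely for the number randomised, 100 per arm.

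**Step 1: how many participants would have a stay.** Assume an admission rate p of 1–10%, equal in both arms. The expected number admitted per arm is 100p. The chance that an arm has fewer than two admitted, and so no within-arm variance, is q = (1−p)^100 + 100p(1−p)^99. The chance that this happens in at least one arm is 1 − (1−q)².

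| Assumed p | Expected admitted per arm | q | At least one arm with fewer than 2 |
|---|---|---|---|
| 1% | 1 | 0.736 | 93% |
| 2% | 2 | 0.403 | 64% |
| 3% | 3 | 0.195 | 35% |
| 5% | 5 | 0.037 | 7% |
| 10% | 10 | 0.0003 | 0.06% |

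For a two-sided t-test at 0.05 with 80% power (noncentral t), the detectable difference is 2.02 SD with 5 admitted per arm and 1.32 SD with 10 per arm.

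**Step 2: can the direction reverse?** Take invented stays per 100 randomised: placebo 3, 3, 3, 12, 12, 12 days; active 12, 12, 12 days. Treatment has prevented the three short admissions and changed nothing else.

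- Among the admitted: placebo 45/6 = 7.5 days, active 36/3 = 12.0 days. Active looks worse by 4.5 days.
- Per randomised participant: placebo 45/100 = 0.45 days, active 36/100 = 0.36 days. Active is better.
- The reversed difference is not significant: p = 0.17 with the pooled t-test, p = 0.08 with Welch's.

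**Step 3: how often, in a scenario chosen to show the problem.** In the control arm, half the admissions are short (mean 2 days) and half long (mean 10 days). Treatment prevents every short admission and cuts the long ones to a mean of 9 days, so it can only help. Stays follow a gamma distribution with shape 2. There are 100 per arm and 20,000 simulated trials per rate. True means among the admitted are (2+10)/2 = 6.0 on control and 9.0 on treatment. Per randomised participant at a 5% control rate they are 0.05 × 6 = 0.30 and 0.025 × 9 = 0.225.

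| | Control rate 4% | 5% | 10% |
|---|---|---|---|
| An arm with fewer than 2 admitted | 46% | 31% | 4% |
| Admitted only: estimate favours placebo (of computable trials) | 72% | 74% | 80% |
| Same, with p < 0.05 (of computable trials) | 11% | 12% | 16% |
| Same, with p < 0.05 (of all trials) | 6% | 8% | 16% |
| Zeros for the never-admitted: estimate favours placebo (of all trials) | 39% | 38% | 34% |
| Same, with p < 0.05 | 0.3% | 0.5% | 0.6% |
| Zeros: favours active with p < 0.05 | 2.5% | 3.7% | 5.8% |

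The rows with zeros used a t-test for comparability. They show the effect of the analysis set, not of a better test.

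**Step 4: sensitivity to the rule for deaths.** Suppose the total also counted every day after death up to day 84. One death on day 14 in the active arm of Step 2 adds 84 − 14 = 70 days. The active mean becomes (36 + 70)/100 = 1.06 against 0.45, so a single event reverses the direction.

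**The case against.** The strongest reply is that the plan is silent rather than wrong. It names no analysis set for stay, and its general intention-to-treat sentence could be meant to give zero days to the never-admitted. A reader might infer that the plan has chosen an analysis that is not intention to treat. The documents do not show that. They leave the set unstated. What stands is that the definition exists only after an admission, and the introduction speaks of stay as time spent once in hospital. Comparing only the admitted is therefore the natural reading.

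A reader might also infer that an in-hospital death would count as a short, good stay. The documents do not say so. Section 6.2.1.4 ends a stay at discharge and is silent on death, so such a stay could be excluded, censored or ended at death. The gap is real, but its consequence is not fixed by the text.

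Third, a reader might infer that a benefit would be reported as harm. That is too strong. The example in Step 2 was built to reverse and is not significant. In the adverse scenario of Step 3, significant wrong-direction results occur in 6–16% of all trials. Admissions and deaths are compared separately, so a reader of the Step 2 results would also see 6 against 3 admissions.

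Finally, the remedy adds little power, and a total that counts days after death can be driven by one event (Step 4). Both objections stand, and the fix takes account of them.

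**Conclusion.** The concern holds in limited form. Followed on its natural reading, the plan tests a secondary outcome in a small group selected by an event after randomisation. This does not fit its own intention-to-treat statement, and it can give an estimate in the wrong direction if treatment prevents mainly short admissions. This goes beyond a missing detail, because the reading the text invites is the one that can mislead.

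The size depends on assumptions: admission rates of 1–10%, the mix of short and long stays, and which admissions treatment prevents. None of these is in the documents, so reversal is possible but not predicted. The primary outcome is unaffected, and the separate comparisons of admissions and deaths limit the damage. The point should be put right before the data are analysed.

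**What to change.** Amend sections 6.2.1.4 and 6.2.2, and align objective 6 in section 2.1.2, as follows.

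- **Comparison:** total inpatient days from randomisation to week 12 in all randomised participants, keeping the present definition of inpatient time.
- **Zeros and missing values:** zero only for participants known not to have been admitted. Unknown status is missing, not zero, and is reported by arm. This matters because admissions are tracked through one hospital's records and phone calls (section 3.6.1), outreach brings in people tested elsewhere (section 4.3.3), and section 5 allows for 10–15% loss to follow-up.
- **Test:** a permutation test or a similar method suited to many zeros, in place of the t-test.
- **Deaths:** state the rule in advance. One option is to report deaths beside inpatient days and use days alive and out of hospital as a sensitivity analysis, since one early death can dominate that total.
- **Stay among the admitted:** description only, without a p-value.

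The cost is modest. Admission and discharge dates must be recorded. The stay definition implies them, but section 3.7 lists only rate, type and length of stay, partly by self-report. The amendment goes to both ethics boards and both Health Canada directorates (section 4.2.3.1). Low power remains: the change restores a comparison of the randomised arms but will not make this outcome decisive.

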6.2.1.5. All-Cause Mortality

The incidence of deaths in both arms will be gathered using medical records and obituary searches.

6.2.2. Statistical Methods

All analyses will follow an intention to treat approach. Continuous and quasi-continuous variables (participant-reported health & health status, primary & secondary severity analyses, and length of stay) will be compared between arms using unadjusted t-tests. Dichotomous outcomes (incidence of severe symptoms, delayed return to usual health, hospitalizations and deaths) will be compared between arms using Chi-square tests or Fisher's exact tests where appropriate. Time to symptom resolution will be displayed graphically with Kaplan-Meier curves and differences between arms will be compared with a log-rank test.

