3.1. Study Design

This study is a double-blind, placebo-controlled, phase III randomized controlled trial powered to detect meaningful differences in the overall health and symptom severity of people with COVID-19 between the treatment and control arms. Eligible participants will be randomly assigned, using a web randomization system, in a ratio of 1:1 to one of the following groups: (1) nutrient therapy with vitamin D, vitamin C, vitamin K2, and zinc or (2) placebo. Total trial duration will be 12 weeks. Nutrients or placebo will be given for a period of 21 days following enrolment and randomization. The length of the intervention period (21 days) encompasses the most common period within which recovery occurs. The median duration of time to symptom resolution is 4-8 days from testing and yet a substantial number of people (26-47%) do not return to their usual state of health within 14-21 days.³³ Available guideline recommendations support a prolonged follow up period in order to assess patients experiencing ongoing symptomatic COVID-19 (signs and symptoms for 4-12 weeks) and those with post-COVID-19 syndrome (signs and symptoms >12 weeks).³⁴

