3.7. Outcome Measurements & Timeline

Participant-Reported Overall Health: measured using the EuroQol visual analogue scale (EQ-VAS).⁵⁹ The EQ-VAS records the respondent’s overall current health on a vertical scale between 0 and 100, where the end points are labelled “the best health you can imagine” (i.e., a score of 100) and “the worst health you

can imagine" (i.e., a score of 0). The EQ-VAS will be filled out each day while on the intervention (21 days total).

Health Status: Measured by combining one level from each of the five dimensions of the EuroQol 5-dimension 5-level (EQ-5D-5L) questionnaire⁵⁹ (mobility, self-care, usual activities, pain/discomfort, and anxiety/depression) to form a unique health state. Each dimension is divided into five levels of perceived problems: 1 – no problem, 2 – slight problems, 3 – moderate problems, 4 – severe problems, and 5 – unable to perform/extreme problems. The EQ-5D-5L questionnaire will be filled in at baseline (i.e., before starting the intervention) and weeks 1, 2, 3, 4, 8, and 12.

Symptom Severity & Duration: Measured using an internally-developed questionnaire specific for the most common COVID-19 symptoms, which include: fever, cough, shortness of breath, fatigue, headache, myalgia/arthralgia (body aches), nausea, vomiting, diarrhea, chills, altered taste, altered smell, and nasal congestion.^{11,60} Each symptom will be rated based on severity with a 4 point scale (0-3): 0-none, 1-slight, 2-moderate, and 3-severe. Participants will fill in this questionnaire each day while receiving treatment (i.e., for 21 days).

The questionnaire is largely based on recommendations from the US Food and Drug Administration (FDA) guidance document for investigators conducting community clinical trials for COVID-19 prevention or treatment.⁶¹ The symptoms were selected based on the most commonly reported COVID-19 symptoms in both the hospital and community setting.^{11,60} Some of the same symptoms are also included in the questionnaire being used in a study of vitamin C and zinc (COVIDAtz) at the Cleveland clinic, potentially allowing for comparison of results.²⁹

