3.7.2. Measurement of Fever

Temperatures will be taken by the participant using a digital oral thermometer provided by the research staff. Participants will be instructed to wait 30 minutes after consumption of any fluids before taking their temperature. Consumption of fluids, especially cold,⁶³ can alter oral temperature readings by clinically meaningful amounts for up to 30 minutes,^{63,64} which, if unaddressed, may lead to measurement errors.

Table 1: Schedule of Events

	Time of Assessment										
	Screening (pre-enrolment)	Baseline (Prior to intervention)	Days 1-6	Day 7	Days 8-13	Day 14	Days 15-20	Day 21	Week 4	Week 8	Week 12
Eligibility	✓										
Informed Consent	✓										
Randomization		✓									
Medical History & Current Medications		✓									
Demographics		✓									
Study Intervention			✓	✓	✓	✓	✓	✓			
EQ-VAS			✓	✓	✓	✓	✓	✓			
Symptom Questionnaire			✓	✓	✓	✓	✓	✓			
EQ-5D-5L		✓		✓		✓		✓	✓	✓	✓
Phone Call Follow-Up • Concomitant Medications • Adverse Events • Hospitalizations • Delayed return to usual health				✓		✓		✓	✓	✓	✓

EQ-VAS: EuroQol Visual Assessment Scale; EQ-5D-5L: EuroQol 5-Dimension 5-Level. EQ-VAS and symptom questionnaires must be filled in on the appropriate days. A 3-day window will be allowed for EQ-5D-5L completion and phone call follow-up for the first 4 weeks. The window will increase to 5 days for weeks 8 and 12. Compliance to the intervention will be participant-reported and take place on day 21 or week 4.

Table 2: Outcome Assessment Methods

Objective	Assessment Method
Participant-reported health	EQ-VAS
Health Status	EQ-5D-5L
Symptom severity & duration of COVID-19 symptoms	Internally developed questionnaire
Incidence of delayed return to usual health	Call with participants
Incidence of Hospitalizations, including ER, acute care, and ICU admissions.	Data will be gathered through medical records and through calls with the participant
Length of Stay	
Incidence of Mortality	Data will be gathered through medical records or through obituary searches if medical records are not available

4. Study Conduct

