4.6. Setting

This study will take place in Ottawa and will involve personnel from the Centre for Health Innovation and The Ottawa Hospital & Ottawa Hospital Research Institute. Day-to-day study activities, including screening & recruitment, outcome collection & follow-up, and product dispensing & tracking, will be managed by study staff at the CHI under the supervision of the principal investigator. The principal investigator will communicate regularly with the qualified investigator and other members of the research team to ensure proper trial conduct. Study interventions will be taken at home by study participants.

5. Sample Size Determination and Power Calculation

With respect to the primary outcome of participant-reported overall health, power calculations were conducted based on between-group differences at a single time point (21 days) and Cohen's guideline for a small effect size of 0.3. A sample size of 176 (88 per arm) provides 80% power to detect a difference at an α of 0.05. To account for an approximate 10-15% lost to follow-up we will enrol 200 participants (100 per arm).

6. Data Collection, Analysis, and Management

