6.2. Data Analysis

6.2.1. Analysis Plan

6.2.1.1. Participant-Reported Overall Health & Health Status

The primary outcome analysis of participant-reported overall health will be conducted using an area under the curve approach comparing the mean difference between arms in the EQ-VAS over the 21-day intervention period. Scores will range from 0-2100 (i.e., 0-100 for 21 days) for each participant.

Health status will be measured using the crosswalk value approach. Each level from each domain of the EQ-5D-5L is aggregated to form a number defining a unique health state, with 11111 (i.e., a “1” in all domains) representing the best possible health status and 55555 (i.e., a “5” in all domains) representing the worst possible health status. Raw values will be converted to an index value out of 1. Differences in mean index values will be compared between arms at various time points over the 12-week study period. Index values will be calculated using the United States crosswalk value set provided by the EuroQol group.^{65,66}

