6.2.1.2. Symptom Severity & Duration

Symptom severity will be conducted using an area under the curve approach comparing the difference in total symptom scores over the 21-day intervention period between both arms. This gives a score range of 0-882 for each participant (i.e., 0-42 each day for 21 days). As a secondary analysis, we will compare the severity of each symptom individually using the same area under the curve approach. Scores for each symptom will range from 0-63 (i.e., 0-3 each day for 21 days). The incidence of severe symptoms (i.e., reporting a “3” for any symptom) will also be compared between arms throughout the intervention period.

The symptom duration analysis will compare the median time to symptom resolution from the start of the intervention period (or the first onset of symptoms if no symptoms were present at the start of the intervention period) up to the end of the intervention period (day 21) between both arms. Symptom resolution will be defined as a zero in all categories with no relapses.

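### The continuous outcomes are tested without adjustment, although a pre-treatment EQ-5D-5L is collected, and no pre-treatment EQ-VAS or symptom score is scheduled; precision of unknown size is given up

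*Combined protocol and SAP*

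**What the plan says.** Section 6.2.2 lists participant-reported health, health status, the severity analyses and length of stay, and states that these "will be compared between arms using unadjusted t-tests". No section names a covariate, a stratification factor or an adjusted sensitivity analysis.

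On what is measured before treatment, Section 3.7 says: "The EQ-5D-5L questionnaire will be filled in at baseline (i.e., before starting the intervention) and weeks 1, 2, 3, 4, 8, and 12". Section 6.2.1.1 gives the index a time-point comparison only: "Differences in mean index values will be compared between arms at various time points over the 12-week study period".

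For the primary instrument, Section 3.7 says: "The EQ-VAS will be filled out each day while on the intervention (21 days total". The symptom questionnaire follows the same daily schedule. Table 1 has no tick for either in the baseline column, and its footnote adds that "EQ-VAS and symptom questionnaires must be filled in on the appropriate days". Nothing says that the day 1 entry comes before the first dose.

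**The concern.** Participants can start in quite different states of health. Entry allows symptom onset up to 7 days earlier and does not require symptoms; the duration analysis in Section 6.2.1.2 provides for the case "if no symptoms were present at the start of the intervention period". Randomisation is blocked but not stratified (Section 4.5). If health before treatment predicts health over the next 21 days, part of the outcome variance can be explained and removed. Adjustment does that with no extra participants and narrows the interval for the treatment effect. An unadjusted t-test leaves that variance in the error term.

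The omission is plainest for the EQ-5D-5L index, where the same instrument is recorded before treatment and at every follow-up. For the EQ-VAS and symptom AUCs, the matching baseline is not collected, and the EQ-5D-5L index is the only substitute.

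**Working it through.** **Inputs from the documents.** Standardised difference d = 0.3, 88 per arm evaluable, 100 per arm enrolled, α = 0.05 (Section 5; sidedness is not stated, two-sided assumed); 1:1 allocation (Section 4.5). Section 5 sets d for "between-group differences at a single time point (21 days"), not for the 21-day AUC, so its use below is illustrative.

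**Assumptions.** The correlation r between baseline covariate and outcome is not given, so a range from 0 to 0.7 is shown. The 5% of missing baselines is also assumed.

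**The plan's own figure.** For two arms and 80% power, n per arm = 2(1.960 + 0.842)²/0.3² = 174.4, rounded up to 175, or 350 in total (176 per arm with the t distribution). The stated total of 176 does not reproduce; it matches the requirement for one arm. At 88 per arm, 0.3 × √(88/2) = 1.990, and power is Φ(1.990 − 1.960) = 51.2%, or 50.8% with the noncentral t. That shortfall is a separate issue; 50.8% is used here only as the starting point.

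**Effect of adjustment.** One covariate with correlation r multiplies the residual SD, and hence the interval width, by √(1 − r²). The effective standardised difference is 0.3/√(1 − r²). Power is from the noncentral t with 174 degrees of freedom unadjusted and 173 adjusted at 88 per arm. The last column is a simulation of the proposed ANCOVA at 88 per arm (20,000 runs), with 5% of baselines missing at random and replaced by the pooled mean.

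| r | Variance removed | Interval width ratio | Effective d | Power, 88 per arm | Power, 100 per arm | Simulated, 5% missing |
|---|---|---|---|---|---|---|
| 0 (as unadjusted) | 0% | 1.000 | 0.300 | 0.508 | 0.560 | 0.507 |
| 0.2 | 4% | 0.980 | 0.306 | 0.524 | 0.577 | 0.519 |
| 0.3 | 9% | 0.954 | 0.314 | 0.546 | 0.600 | 0.540 |
| 0.5 | 25% | 0.866 | 0.346 | 0.627 | 0.684 | 0.619 |
| 0.7 | 49% | 0.714 | 0.420 | 0.791 | 0.840 | 0.772 |

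Three readings follow.

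- **Cost when the covariate is useless.** At r = 0 and 88 per arm, the lost degree of freedom leaves power at 0.508.
- **Value when it is useful.** At r = 0.5, 176 participants carry the information of 176/(1 − 0.25), about 235.
- **Limit.** Reaching 80% power needs r = 0.708 at 88 per arm or 0.657 at 100 per arm. With 5% of baselines replaced by the mean, r² is scaled by 0.95, so the values become 0.708/√0.95 = 0.73 and 0.657/√0.95 = 0.67.

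Simulated type I error of the ANCOVA with the missing-baseline rule was 0.049 to 0.052 (10,000 runs per setting).

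**The case against.** The strongest reply is that nothing here is an error. The plan states its method openly, the method is valid, and the gain cannot be quantified. The gain is also least certain for the primary outcome, because the only baseline now collected is a different instrument. At r of 0.2 to 0.3 it adds about 2 to 4 percentage points of power, and nothing in the documents supports 0.5 or 0.7. Section 3.1 also reports: "The median duration of time to symptom resolution is 4-8 days from testing". Quick recovery could weaken the link between baseline and a 21-day AUC.

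Most of this stands, and it is why the point is about efficiency. But the same section says that 26-47% are not back to usual health by 14-21 days, so the correlation may equally be substantial. The balance is one-sided: almost nothing is lost if the covariate is useless.

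Three practical objections also stand, and they shape the fix:

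- The statistical methods are part of the protocol, so even a wording change falls under the amendment review in Section 4.2.3.1.
- Baseline forms added after enrolment has begun would be missing for everyone already enrolled. The simulation covers only 5% missing.
- The symptom diary covers fever, and Section 3.7.2 relies on a thermometer that the study supplies. The documents do not say that participants have it before the first dose.

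**Conclusion.** The point holds. A pre-treatment EQ-5D-5L is collected and given no covariate role, and neither the EQ-VAS nor the symptom diary has a scheduled pre-treatment value. The result is a loss of precision with no bias, and its size cannot be fixed from the documents. Under the assumed range of r from 0.2 to 0.7, intervals would be about 2% to 29% narrower. Power at d = 0.3 and 88 per arm would rise from 51% to between 52% and 79% with complete baselines, and slightly less with some missing.

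The plan should make this change, but its results would not be invalid without it. Adjustment cannot be relied on to repair Section 5, since that would need r of about 0.7.

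**What to change.** **In Section 6.2.2**, prespecify before unblinding one linear model per outcome, with arm and one baseline covariate. Report the adjusted mean difference with its 95% confidence interval. Keep the unadjusted t-test as supportive.

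- **Covariate.** Use the baseline EQ-5D-5L index for the EQ-VAS AUC (primary), for the symptom AUCs, and for the EQ-5D-5L index at each follow-up time point.
- **Missing baseline.** If the value is missing or was recorded after the first dose, replace it by the mean of the observed baseline values pooled over arms. No randomised participant is then dropped for a missing covariate.
- **Left out.** Do not include days since symptom onset; participants without symptoms have no value for it. Length of stay is not part of this change, because it exists only for hospitalised participants.

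**Preferably also**, add the EQ-VAS and one symptom diary to the baseline column of Table 1, completed before the first dose. Baseline EQ-VAS then becomes the single covariate for the primary AUC, and the baseline symptom score the single covariate for the symptom AUCs. The text should say whether each single-symptom AUC uses its own baseline item or the total; the matching item is the natural choice. If the forms cannot be in place before the first enrolment, keep the EQ-5D-5L index as the covariate for everyone.

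**Cost.** The EQ-5D-5L adjustment needs wording in Section 6.2.2 and no new data. The addition needs one EQ-VAS item and one diary page per participant, matching edits to Section 3.7 and Table 1, and a thermometer in hand at baseline. Either change goes through both research ethics boards and the two Health Canada directorates as an amendment (Section 4.2.3.1).
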